## 9.12 Study endpoints

### 9.12.1 Primary endpoint

The primary efficacy endpoint is the time from randomization to the first recurrent thromboembolic event.

A thromboembolic event is a confirmed recurrent proximal DVT or PE, that means the composite of:

a) ipsilateral proximal DVT of the lower limbs (symptomatic or unsuspected):

A recurrent proximal DVT must be distinguished from the original thrombus by comparing serial imaging modalities (compression ultrasonography, venography, CT venography, or MR venography). In order to be classified as a recurrent event, there must be one or more new filling defect seen on the second imaging test but not evident on the original images, or on an interval imaging test showing thrombus resolution; only in symptomatic patients, if the venous segment was non-compressible at randomization, a substantial increase (4 mm or more) in diameter of the thrombus during full compression.

b) contralateral proximal DVT of the lower limbs (symptomatic or unsuspected):

In order to be classified as a recurrent event, there must be one or more new filling defects at compression ultrasonography, venography, CT venography, or MR venography. Unsuspected thrombus must be evident on the second imaging test and not evident on the original images.

c) DVT of the upper limbs (symptomatic):

In order to be classified as a recurrent event, there must be one or more new filling defects at compression ultrasonography, venography, CT venography, or MR venography.

**d) pulmonary embolism (symptomatic or unsuspected):**

- Symptoms of PE with one of the following findings:

- a new intraluminal filling defect at CT pulmonary angiography;
- a new intraluminal filling defect, or an extension of an existing defect, or a new sudden cut-off of vessels more than 2.5 mm in diameter at pulmonary angiogram;
- a new perfusion defect of at least 75% of a segment with a local normal ventilation result (high probability) on ventilation/perfusion lung scan (VQ scan);
- inconclusive CT pulmonary angiography, pulmonary angiography, or VQ scan evidence of a new or recurrent PE with demonstration of a new or recurrent DVT in the lower extremities by compression ultrasonography or venography.

- Fatal PE defined as PE based on objective diagnostic testing before death or autopsy; death where PE is the most probable cause of a sudden and unexplained death according to central adjudication.

- In unsuspected PE, in order to be classified as a recurrent event, there must be one or more new filling defect in segmental or more-proximal arteries at CT pulmonary angiography evident on the second study not appreciated on previous images or an interval study clearly showing emboli resolution.

**9.12.2 Secondary efficacy endpoints**

1. The individual components of the primary efficacy outcome:
  - a. Time from randomization to the first recurrent ipsilateral proximal DVT of the lower limbs (symptomatic or unsuspected)
  - b. Time from randomization to the first recurrent contralateral proximal DVT of the lower limbs (symptomatic or unsuspected)
  - c. Time from randomization to the first recurrent DVT of the upper limbs (symptomatic)
  - d. Time from randomization to the first recurrent pulmonary embolism (symptomatic or unsuspected)
2. Time from randomization to the first symptomatic recurrent thromboembolic event.
3. Time from randomization to the composite of primary efficacy outcome plus major bleeding (whichever occurs first).
4. Time from randomization to death (all causes) (Overall Survival).
5. Time from randomization to the composite of primary efficacy outcome plus major bleeding plus death (all causes) (whichever occurs first).
6. Time from randomization to the occurrence of any fatal or not fatal cardiovascular event.
7. Time from randomization to thromboembolic events at sites other than DVT and PE (i.e. ischemic stroke, myocardial infarction, other venous thromboembolic events or other arterial thromboembolic events)
8. Total score and subscales of the Anti-Clot Treatment Scale (ACTS, a Quality of life evaluation).

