- 21) any condition that, as judged by the investigator, would place the subject at increased risk of harm if he/she participated in the study.

Efficacy Study Outcomes:

Primary efficacy outcome: objectively confirmed recurrent VTE occurring during the study treatment period, that means the composite of:

- proximal DVT of the lower limbs (symptomatic or unsuspected)
- DVT of the upper limb (symptomatic)
- PE (symptomatic or unsuspected)

Secondary efficacy outcomes:

- the individual components of the primary efficacy outcome;
- symptomatic recurrence of VTE;
- all cause death;
- the composite of primary efficacy outcome plus major bleeding;
- the composite of primary efficacy outcome plus major bleeding plus all cause death;
- the composite of primary efficacy outcome plus all cause death:
- any major cardiovascular event, fatal or non-fatal (including acute myocardial infarction or ischemic stroke);
- all venous thromboembolic events (including splanchnic vein thrombosis and cerebral vein thrombosis):
- Quality of life (QoL) according to Anti-Clot Treatment Scale (ACTS) (see Appendix 2)

Safety Study Outcomes:

Primary safety outcome is major bleeding, defined (as per ISTH guidelines), as acute clinically overt bleeding associated with one or more of the following:

- decrease in hemoglobin of 2 g/dl (1.2 mmol/L) or more;
- transfusion of 2 or more units of packed red blood cells;

- bleeding that occurs in at least one critical site [intracranial, intra-spinal, intraocular (within the corpus of the eye; thus, a conjunctival bleed is not an intraocular bleed), pericardial, intraarticular, intramuscular with compartment syndrome, or retroperitoneal];
- bleeding that is fatal;
- bleeding that necessitates acute surgical intervention

Secondary safety outcomes include:

- Clinically relevant non-major bleeding event defined as acute clinically overt bleeding that does not meet the criteria for major and consists of:
 - any bleeding compromising hemodynamics;
 - spontaneous hematoma larger than 25 cm², or 100 cm² if there was a traumatic cause:
 - intramuscular hematoma documented by ultrasonography;
 - epistaxis or gingival bleeding requiring tamponade or other medical intervention or bleeding from venipuncture for >5 minutes:
 - hematuria that was macroscopic and was spontaneous or lasted for more than 24 hours after invasive procedures;

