- In unsuspected PE, in order to be classified as a recurrent event, there must be one or more new filling defect in segmental or more-proximal arteries at CT pulmonary angiography evident on the second study not appreciated on previous images or an interval study clearly showing emboli resolution.

The secondary efficacy outcomes of the study are:

- the individual components of the primary efficacy outcome;
- symptomatic recurrence of VTE;
- all cause death;
- the composite of primary efficacy outcome plus major bleeding;
- the composite of primary efficacy outcome plus major bleeding plus all cause death;
- the composite of primary efficacy outcome plus all cause death;
- any major cardiovascular event, fatal or not fatal (including acute myocardial infarction¹ or ischemic stroke²);
- all venous thromboembolic events (including splanchnic vein thrombosis and cerebral vein thrombosis both objectively assessed);
- Quality of Life (QoL), assessed by means of the Anti-Clot Treatment Scale (ACTS) (see Appendix 2).

¹ An acute myocardial infarction requires the presence of at least 2 out of the 3 following conditions:

⁻ an appropriate clinical situation suggestive of a myocardial infarction (eg, abnormal history, physical examination or new ECG changes)

⁻ elevation of CK-MB or Troponin T or I ≥ 2 x ULN; if no CK-MB or troponin values are available, a total CK ≥2x ULN

⁻ new, significant (≥0.04 seconds) Q waves in ≥ 2 contiguous leads.

² An acute stroke is defined as a new, focal neurological deficit of sudden onset, lasting at least 24 hours, that is not due to a readily identifiable non-vascular cause (i.e., brain tumor, trauma). All strokes during the study will be assessed by imaging or autopsy and classified as primary hemorrhagic, non-hemorrhagic, infarction with hemorrhagic conversion, or unknown, as defined by the American College of Cardiology (ACC).

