- Composite of primary efficacy outcome plus major bleeding plus all cause death: Event free survival will be estimated according to Kaplan-Meier and the event free survival in the two treatment groups will be compared by means of a Cox's proportional hazard model with treatment group and center as dummy covariates. The apixaban-to-comparator Hazard Ratio will be computed with associated two-sided 95% confidence interval.
- Composite of primary efficacy outcome plus all cause death: Event free survival will be estimated according to Kaplan-Meier and the event free survival in the two treatment groups will be compared by means of a Cox's proportional hazard model with treatment group and center as dummy covariates. The apixaban-to-comparator Hazard Ratio will be computed with associated two-sided 95% confidence interval.
- Any fatal or not fatal cardiovascular event: The same competing risk model (23) defined above for the analysis of primary efficacy variable will be employed for the analysis of the time from randomization to the occurrence of any fatal or not fatal cardiovascular event. The apixaban-to-comparator Hazard Ratio adjusted for the competing risk of death unrelated to cardiovascular event will be computed with associated two-sided 95% confidence interval.
- All venous thromboembolic events (including splanchnic vein thrombosis and cerebral vein thrombosis): The same competing risk model (23) defined above for the analysis of primary efficacy variable will be employed for the analysis of the time from randomization to thromboembolic events at sites other than DVT and PE. The apixaban-to-comparator Hazard Ratio adjusted for the competing risk of death unrelated to venous thromboembolic events will be computed with associated two-sided 95% confidence interval.
- Quality of life evaluation (ACTS Scale) (see Appendix 2): For the total score and for each of the subscales, a linear effects model will be estimated with treatment group and center as dummy fixed effects. Results will be reported as Least-Square Means together with associated two-tailed 95% CI and p-value. ITT Analyses will be performed with missing data imputed using conventional LOCF.

Multiplicity

No adjustment for multiplicity is required for the primary efficacy analysis because it is focused on a single time point (6-month) at which only two treatments are being compared.

Center-to-center variability

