#### Concerning efficacy

- 1) To assess whether oral apixaban is non-inferior to the subcutaneous dalteparin for the treatment of acute proximal deep vein thrombosis (DVT) and/or pulmonary embolism (PE) in patients with cancer, with respect to one of the following, taken individually:
  - a. Recurrence of proximal DVT of the lower limbs (symptomatic or unsuspected)
  - b. Recurrence of DVT of the upper limbs (symptomatic)
  - c. Recurrence of pulmonary embolism (symptomatic or unsuspected)
- 2) To assess whether oral apixaban is non-inferior to the subcutaneous dalteparin for the treatment of acute proximal DVT and/or pulmonary embolism (PE) in patients with cancer, with respect to symptomatic recurrence of Venous Thromboembolism (VTE).
- 3) To assess whether oral apixaban is non-inferior to the subcutaneous dalteparin for the treatment of acute proximal deep vein thrombosis (DVT) and/or pulmonary embolism (PE) in patients with cancer, with respect to confirmed recurrence of proximal DVT or PE plus major bleeding.

- 4) To compare the overall survival between the two treatment groups (all causes of death).
- 5) To compare the event free survival between the two treatment groups, where the event is a composite of the primary efficacy outcome plus major bleeding plus death due to all causes.
- 6) To compare the event free survival between the two treatment groups, where the event is a composite of the primary efficacy outcome plus death due to all causes.
- 7) To compare oral apixaban with the subcutaneous dalteparin for the treatment of acute proximal deep vein thrombosis (DVT) and/or pulmonary embolism (PE) in patients with cancer, with respect to any fatal or not fatal cardiovascular event (including acute myocardial infarction or ischemic stroke).
- 8) To compare oral apixaban with the subcutaneous dalteparin for the treatment of acute proximal deep vein thrombosis (DVT) and/or pulmonary embolism (PE) in patients with cancer, with respect to all venous thromboembolic events (including splanchnic vein thrombosis and cerebral vein thrombosis).
- 9) To compare quality of life evaluation between the two treatment groups (ACTS Scale).

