- Any fatal or not fatal cardiovascular event: The competing risk model defined in paragraph 10.8.1 for the analysis of primary efficacy variable will be employed for the analysis of the time (in days) from randomization to the occurrence of any fatal or not fatal cardiovascular event. The apixaban-to-comparator Hazard Ratio adjusted for the competing risk of death unrelated to cardiovascular event will be computed with associated two-sided 95% confidence interval. Number and percentage of events of interest, competing events and censored patients will be presented as summary of failure outcome. Degrees of freedom (DF), Wald Chi-square and the associated p-value derived from the PHREG model will be also presented. Subjects with no events at the end of the study will be censored at the date of the last contact.
- All venous thromboembolic events (including splanchnic vein thrombosis and cerebral vein thrombosis): The same competing risk model defined in paragraph 10.8.1 for the analysis of primary efficacy variable will be employed for the analysis of the time (in days) from

randomization to thromboembolic events at sites other than DVT and PE. The apixaban-to-comparator Hazard Ratio adjusted for the competing risk of death unrelated to venous thromboembolic events will be computed with associated two-sided 95% confidence interval. Number and percentage of events of interest, competing events and censored patients will be presented as summary of failure outcome. Degrees of freedom (DF), Wald Chi-square and the associated p-value derived from the PHREG model will be also presented. Subjects with no events at the end of the study will be censored at the date of the last contact.

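### The secondary outcome labelled as all venous thromboembolism is timed only on events outside DVT and PE, and its label, event list and competing event do not agree

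*SAP*

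**What the plan says.** **The label.** The protocol synopsis lists the outcome as "all venous thromboembolic events (including splanchnic vein thrombosis and cerebral vein thrombosis"). Protocol 5.1 has the same outcome and asks for objective assessment: "all venous thromboembolic events (including splanchnic vein thrombosis and cerebral vein thrombosis both objectively assessed"). SAP 5.2, efficacy objective 8, compares the arms "with respect to all venous thromboembolic events (including splanchnic vein thrombosis and cerebral vein thrombosis"). Protocol 10.6 and SAP 10.8.2 use the same label as the heading of the analysis.

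**The timed event.** Under that heading, Protocol 10.6 analyses the "time from randomization to thromboembolic events at sites other than DVT and PE", and SAP 10.8.2 likewise counts from "randomization to thromboembolic events at sites other than DVT and PE".

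**The endpoint list.** SAP 9.12.2 item 7 does not carry the all-venous label. It defines its event as "thromboembolic events at sites other than DVT and PE (i.e. ischemic stroke, myocardial infarction, other venous thromboembolic events or other arterial thromboembolic events").

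**The competing event.** In SAP 10.8.2 the hazard ratio is "adjusted for the competing risk of death unrelated to venous thromboembolic events"; Protocol 10.6 says the same. SAP 10.8.2 then censors subjects without an event at their last contact.

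**The concern.** A label that promises all venous events includes DVT and PE on any plain reading. The analysis text under that label takes them out, and the endpoint list adds stroke, myocardial infarction and other arterial events, which are not venous. No item in SAP 9.12.2 covers all venous events, so objective 8 has no matching endpoint.

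Two programmers could each follow part of the text and produce different hazard ratios under one title. The trial is open-label, so the definition should be fixed before anyone can see how the choice affects the result. The competing event adds a second problem: it was written for the label, and it leaves some deaths wrongly handled once DVT and PE are excluded.

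**Working it through.** The finding rests on the wording. I first compared the definitions, then illustrated the scale.

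**Step 1. The same patient under each definition**

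| Patient's first event | Label (synopsis, 5.1, objective 8) | Analysis text (Protocol 10.6, SAP 10.8.2) | SAP 9.12.2 item 7 |
|---|---|---|---|
| Recurrent proximal DVT, non-fatal | Event | Not an event | Not an event |
| Splanchnic vein thrombosis | Event | Event | Event |
| Myocardial infarction, non-fatal | Not an event | Arterial events not named | Event |
| Myocardial infarction, fatal | Competing death | Competing death, by its competing-event wording | Event |
| Fatal PE | Event | Neither event nor competing | Not an event |

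Only the splanchnic row agrees throughout.

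**Step 2. Fatal PE**

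SAP 9.12.1 counts such deaths within the primary outcome: "Fatal PE defined as PE based on objective diagnostic testing before death or autopsy", or as the most probable cause of a sudden unexplained death. A fatal PE is related to venous thromboembolism, so it is not a competing event here. It is also at an excluded site, so it is not an event of interest. What remains is the SAP 10.8.2 default, censoring at last contact. A Fine and Gray model should not treat a death as ordinary censoring.

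A similar gap exists in the component analyses (Protocol 10.6, SAP 10.8.2), where the competing event is death not related to VTE. For time to lower-limb or upper-limb DVT, a fatal PE is again neither. The SAP default there is censoring at the 6-month follow-up, which such a patient does not reach.

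**Step 3. Reproducing the plan's figures**

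Inputs from Protocol 10.1: margin 2.00, one-sided alpha 0.025, power 80%, rate 7%. True hazard ratio 1 and 1:1 allocation.

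- Events: 4 × (1.960 + 0.842)² / (ln 2)² = 65.3
- Patients: 65.3 / 0.07 = 933.5, so 934
- Inflated: 934 / 0.80 = 1,167.5, so 1,168

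Both totals match the plan. They are used here only as a base for scale.

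**Step 4. Illustration of scale**

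The documents give no rate for venous events at other sites. I assume 0.5% to 2% at 6 months, 7% DVT/PE in both arms, 934 patients, and no patient with both types.

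- DVT/PE events: 0.07 × 934 = 65.4
- Other-site venous only: 0.005 × 934 = 4.7 to 0.02 × 934 = 18.7
- All venous: 65.4 + 4.7 = 70.1 to 65.4 + 18.7 = 84.1
- DVT/PE share of all venous: 65.4 / 70.1 = 93% to 65.4 / 84.1 = 78%

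The item 7 list would give more than the other-site venous count because it includes arterial events. If these also ran at an assumed 0.5% to 2%, the list would hold 0.010 × 934 = 9.3 to 0.040 × 934 = 37.4 events.

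I give no confidence-interval widths. The planned model includes centre, with sites pooled only to at least 12 patients, and both stratification factors; with this few events it may not be estimable. SAP 10.8.2 also follows patients to last contact for this endpoint, whereas these counts are for 6 months.

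**The case against.** **An other-site endpoint may have been intended.** Both documents use the same exclusion. Protocol 9.2.1 and SAP 10.9.1.1 treat venous thrombosis at other locations as its own category. This is plausible and it stands. But in that case the synopsis, Protocol 5.1, objective 8 and both analysis headings are mislabelled, the competing event still does not fit, and the arterial list still conflicts with the heading. Neither reading makes the text consistent. A reader might infer that the exclusion is the slip; the documents do not show which side is.

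**Item 7 may be a separate endpoint.** SAP 9.12.2 is incomplete: it also omits the composite of the primary outcome plus all-cause death, which objective 6 and SAP 10.8.2 include. Item 7 is linked to the all-venous analysis through shared wording, not a shared title. This limits what item 7 proves, but the contradiction inside Protocol 10.6 and SAP 10.8.2 does not depend on it.

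**DVT and PE are analysed elsewhere.** This is true for primary-outcome events, so a reader who inferred that these events are lost to the trial would be wrong. It is not the whole answer. SAP 10.9.1.1 records distal veins as a DVT location, while the primary outcome takes only proximal lower-limb and symptomatic upper-limb DVT. Isolated distal DVT and unsuspected upper-limb DVT therefore lie outside both the primary outcome and the other-site event.

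**The output shells may settle it.** SAP section 14 refers to them as a separate document, which was not available. The actual programming cannot be judged, but the SAP should still be consistent on its own.

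**Conclusion.** The inconsistency is established from the text with high confidence and needs no assumed rate. As written, a hazard ratio titled all venous would contain no DVT or PE, and objective 8 would not be answered. It should be corrected before results are seen.

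Three stronger readings are not supported:

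- That the main result is at risk. The primary analysis, margin and sample size do not depend on this endpoint.
- That fatal PE has no coding at all. The default censors it at last contact; the fault is that this is the wrong treatment of a death. Nor is the gap confined to this endpoint, since a similar one arises in the DVT component analyses.
- That about 5 to 19 events describes item 7. That count is for venous events only; the item 7 list is longer.

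The contrast of about 70 to 84 events against about 5 to 19 is illustrative. It rests on the assumed other-site rate, the planned 7% in both arms and 934 patients. It shows only that one label could cover two very different amounts of information.

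**What to change.** Before results are seen, choose one event set and make the label, event list and competing event agree in Protocol 10.6, SAP 9.12.2 item 7 and SAP 10.8.2.

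- **(a) To answer objective 8 as stated:** count the first objectively confirmed venous event at any site, meaning primary-outcome events plus splanchnic, cerebral and other venous thrombosis. State whether isolated distal DVT and unsuspected upper-limb DVT count. Take arterial events out of this endpoint. Myocardial infarction and ischemic stroke already belong to the cardiovascular endpoint (item 6); state where other arterial events are analysed.
- **(b) If other-site events were intended:** relabel the outcome in the synopsis, Protocol 5.1 and 10.6, SAP objective 8 and SAP 10.8.2, and state whether arterial events count.
- **In either case, and for the DVT component analyses:** code every death that is not itself a counted event as a competing event rather than censoring it. This includes fatal PE wherever it is not counted.

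The cost is a SAP revision, re-derivation of this endpoint, recoding of deaths in the DVT components, and a protocol amendment or a difference documented in the SAP. The shells should be checked against the chosen definition. No new data are needed: SAP 10.1 and 10.9.1.1 already record other venous and other arterial events as separate categories.
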